14.2.4.5 Programming rules

The following should be used for programming of efficacy results:

14.2.4.5.1 Calculation of 'time to event' variables

Time to event = end date - start date + 1 (in days)

When no post-baseline tumor assessments are available, the date of randomization/start of treatment will be used as end date (duration = 1 day) when time is to be censored at last tumor assessment, i.e. time to event variables can never be negative.

14.2.4.5.2 Incomplete assessment dates

All investigation dates (e.g. X-ray, CT scan) must be completed with day, month and year.

If one or more investigation dates are incomplete but other investigation dates are available, this/these incomplete date(s) are not considered for calculation of the assessment date (and assessment date is calculated as outlined in [Section 14.2.3.2.7](#)). If all measurement dates have no day recorded, the 1st of the month is used.

If the month is not completed, for any of the investigations, the respective assessment will be considered to be at the date which is exactly between previous and following assessment. If a previous and following assessment is not available, this assessment will not be used for any calculation.

14.2.4.5.3 Incomplete dates for last known date patient alive or death

All dates must be completed with day, month and year. If the day is missing, the 15th of the month will be used for incomplete death dates or dates of last contact.

14.2.4.5.4 Non-target lesion response

If no non-target lesions are identified at baseline (and therefore not followed throughout the study), the non-target lesion response at each assessment will be considered 'not applicable (NA)'.

14.2.4.5.5 Study/project specific programming

The standard analysis programs need to be adapted for each study/project.

14.2.4.5.6 Censoring reason

In order to summarize the various reasons for censoring, the following categories will be calculated for each time to event variable based on the treatment completion page, the study evaluation completion page and the survival page.

For survival the following censoring reasons are possible:

- Alive
- Lost to follow-up

For PFS and TTP (and therefore duration of responses) the following censoring reasons are possible:

- Ongoing without event
- Lost to follow-up
- Withdraw consent
- Adequate assessment no longer available*
- Event documented after two or more missing tumor assessments (optional, see [Table 14-9](#))
- Death due to reason other than underlying cancer (*only used for TTP and duration of response*)
- Initiation of new anti-cancer therapy

*Adequate assessment is defined in [Section 14.2.3.2.7](#). This reason is applicable when adequate evaluations are missing for a specified period prior to data cut-off (or prior to any other censoring reason) corresponding to the unavailability of two or more planned tumor assessments prior to the cut-off date. The following clarifications concerning this reason should also be noted:

- This may be when there has been a definite decision to stop evaluation (e.g. reason="Sponsor decision" on study evaluation completion page), when patients are not followed for progression after treatment completion or when only UNK assessments are available just prior to data cut-off).
- The reason "Adequate assessment no longer available" also prevails in situations when another censoring reason (e.g. withdrawal of consent, loss to follow-up or alternative anti-cancer therapy) has occurred more than the specified period following the last adequate assessment.
- This reason will also be used to censor in case of no baseline assessment.

14.3 Appendix 3: ALK Immunohistochemistry

The population for this study includes adult Chinese patients with locally advanced or metastatic NSCLC harboring a confirmed ALK rearrangement, defined as positive using the FDA approved Vysis ALK Break Apart FISH Probe Kit (Abbott Molecular Inc.) test and scoring algorithm (including positivity criteria) or positive as assessed by the CFDA approved immunohistochemistry (IHC) test (Ventana Medical Systems, Inc) using rabbit monoclonal primary antibody assay (D5F3) and associated scoring algorithm. If documentation of ALK rearrangement is not available as described above, a test to confirm ALK rearrangement must be performed using an archival tumor obtained at or since the time of diagnosis or a new tumor biopsy obtained prior to the first LDK378 dose. The test will be performed at a Novartis designated central laboratory (by IHC test using rabbit monoclonal primary antibody assay (D5F3), Ventana Medical Systems, Inc). Patients must wait for the result of the ALK rearrangement status before initiating treatment with LDK378.

Overview

The VENTANA anti-ALK (D5F3) Rabbit Monoclonal Primary Antibody (VENTANA anti-ALK (D5F3) IHC assay will be used to determine ALK IHC status and to select ALK-positive patients for enrollment in Study [CLDK378A2301]. The anti-ALK (D5F3) rabbit monoclonal antibody IHC assay is currently being developed by Ventana Medical Systems as a companion diagnostic to LDK378. For study CLDK378A2301, the VENTANA anti-ALK (D5F3) assay will be used for investigational purposes only. VENTANA anti-ALK (D5F3) is intended for laboratory use in the detection of the anaplastic lymphoma kinase (ALK) protein in formalin-fixed, paraffin-embedded (FFPE) non-small cell lung cancer (NSCLC) tissue stained with a VENTANA BenchMark XT® immunohistochemical (IHC) automated slide stainer. It is indicated as an aid in identifying patients eligible for treatment with LDK378.

Device Description

The VENTANA anti-ALK (D5F3) IHC assay is an automated IHC staining assay system comprising a pre-diluted, ready-to-use anti-ALK (D5F3) rabbit monoclonal primary antibody, the BenchMark® XT automated slide-staining platform, OptiView DAB detection kit, OptiView Amplification kit, Rabbit Monoclonal Negative Control Ig and VENTANA anti-ALK 2-in-1 cell line control slides. The reagents and the IHC procedure are optimized for use on the BenchMark XT® automated slide stainer, utilizing NexES software (Ventana System Software).

Scoring System

The IHC scoring system evaluates specific VENTANA anti-ALK (D5F3) staining in NSCLC tumor cells by the presence of a strong, granular, cytoplasmic staining pattern. Pathologists must rely on the Negative Reagent Control (NRC) slides to distinguish non-specific staining from specific ALK positivity. Samples must be assessed for morphological damage and the presence of viable tumor versus necrosis. Light, granular, cytoplasmic stippling in alveolar macrophages can occur on anti-ALK (D5F3) and/or NRC slides as an artifact of the detection system. This staining artifact should be noted on the Slide Evaluation Form comment field but

should NOT be interpreted as ALK-positive staining. Some background staining has also been observed on normal mucosa in NSCLC specimens, as well as in necrotic tumor areas; this staining also should not be interpreted as ALK-positive staining. Case slide sets failing to show specific staining of the case tissue with VENTANA anti-ALK (D5F3) as defined in the following table cannot be considered ALK-positive.

Table 14-10 Clinical Interpretation of VENTANA anti-ALK (D5F3) Staining

Clinical Interpretation	Staining Description
Positive for ALK	
Presence of strong granular cytoplasmic staining in tumor cells (any percentage of positive tumor cells).
 
Known staining artifacts should be excluded, including:
 
light cytoplasmic stippling in alveolar macrophages,cells of neural origin (nerve and ganglion cells),glandular epithelial staining, andcells within lymphocytic infiltrate. 
Some background staining also may be observed within normal mucosa in NSCLC (including mucin) and in necrotic tumor areas, which also should be excluded from the clinical evaluation.

Negative for ALK	Absence of strong granular cytoplasmic staining in tumor cells.

14.4 Appendix 4: Cockcroft-Gault formula

Female:

$$GFR[\text{ml / min}] = 0,85 \cdot \frac{(140 - \text{age}[\text{y}]) \cdot \text{bodyweight}[\text{kg}]}{72 \cdot \text{serum creatinine} [\text{mg / dl}]}$$

Male:

$$GFR[\text{ml / min}] = \frac{(140 - \text{age}[\text{y}]) \cdot \text{bodyweight}[\text{kg}]}{72 \cdot \text{serum creatinine} [\text{mg / dl}]}$$

Clinical Development

LDK378

CLDK378A2109 / NCT02040870

A phase I/II multicenter, open-label, single-arm study of LDK378, administered orally in adult Chinese patients with ALK-rearranged (ALK-positive) advanced non-small cell lung cancer (NSCLC) previously treated with crizotinib

Statistical Analysis Plan (SAP)

Author: [REDACTED]

Document type: SAP Documentation

Document status: Final 1.0

Release date: 13-Feb-2017

Number of pages: 61

Property of Novartis
Confidential

May not be used, divulged, published or otherwise disclosed
without the consent of Novartis

Document History – Changes compared to previous version of RAP module 3.

Version	Date	Changes
V2.0	05-Jun-2014	Final version 2.0
Amendment 1	17-Dec-2014	The content and language of this RAP document were modified to align with protocol amendment 1 and to align with the analyses implemented in other LDK378 studies. Further details are described below:
		Section 2.4: [REDACTED] [REDACTED] [REDACTED]
		Figure 1.1: Number updated to reflect the sample size change.
		Section 3.1.1.6 Derivation rules for baseline (including ECG) were further clarified.
		Section 3.1.2: Updated timing primary CSR analysis to be after all patients completed 24 weeks (6 cycles) of treatment.
		Section 3.1.3: “Efficacy analysis set” definitions were added for the efficacy population used for interim analysis.
		A new major PD “Patient has been previously treated with more than 2 lines of chemotherapy” was added.
		Added criteria that patient should take study drug according to the original assigned dose for at least 5 consecutive days without interruption or dose modification prior to the PK sampling day (except for PK run-in Day 1 for patients with extensive assessment) for evaluable full PK profile
		Section 3.1.4 Table of patients classification rules are added.
		Section 3.2.2 & Section 3.2.6: Version information added to MedDRA and WHO drug dictionary.

Version	Date	Changes
		Section 3.2.8: Clarification added for pharmacokinetic analysis using PAS. [REDACTED]
		CLss/F is added as a secondary parameter for PK analysis.
		Section 3.2.9.1, Section 3.2.8: Minor changes to adverse event section to align with protocol amendment 01 and LDK378 program.
		Section 3.2.9.2 The wording for the derivation of CTC grading for laboratory values was clarified and corrected to cover cases such as creatinine increased grading when the post-baseline value is \leq ULN
		Section 3.2.9.4. Added shift tables for ECOG status from baseline to best post baseline.
		Section 3.3: [REDACTED] [REDACTED]
		Section 3.4: Confidence interval provided for the larger sample size.
		Section 4.1.1: This section is removed as this RAP now is in alignment with the new updated protocol.
		Section 4.2.2: Source of ORR derived based on the raw data per investigator was removed. This source is used only for data cleaning purposes.
		Section 4.3: Categories to describe whether the questionnaire was completed were updated to align with CRF.
		Section 4.4: More details and clarification added for PK analyses.

Version	Date	Changes
		
Appendix 1: Tables/Listings on concomitant medications and significant non drug therapies were split into separate listings as per NCDS.
 
The list of output for IA was updated.

Amendment 2	18-Jan-2016	
Naming conventions have been updated for some outputs to align with LDK378 program.
 
Section 2.4:
 
Updates in study design section to remove “start of a new anti-cancer therapy” from the list of allowable reasons to stop collection of tumor assessments to align with protocol amendment 2. 
Section 3.1
 
The major inclusion/exclusion criteria leading to exclusion from PPS were updated in 3.1.3 per team discussion; the classification rules in section 3.1.4 were updated and further clarified. 
Section 3.2
 
Listing of ALK status in section 3.2.2 was removed as the same has been mentioned in the [REDACTED]Updates in the PK parameter table to align with protocol v03.Additional AE summaries were added and the list of AESI's was updated in Sec 3.2.9.1.The list of laboratory values to be summarized was updated in section 3.2.9.2.Denominator for new abnormality post baseline ECGs were clarified in Section 3.2.9.3. The interval to define “lost to follow up” for overall survival was updated to 18 weeks per LDK phase II practice.[REDACTED][REDACTED]Section 4.1:Clarification on the handling of missing date in section 4.1.2.

Section 4.2

Version	Date	Changes
		
Clarified that change in contrast use in conventional or spiral CT is not considered a change in modality in Sec 4.2.1.The language on PFS censoring rules was updated in Sec 4.7.1.Updated the guidelines for the display of the waterfall graph in Sec 4.2.1.

1.1 Document content

This Statistical Analysis Plan (SAP) describes the planned statistical analysis methods for the final clinical study report of LDK378A2109. It is structured as

- a draft of Section 9.7 (Statistical methods planned in the protocol and determination of sample size) of the clinical study report (CSR)
- and also a draft of Appendix 16.1.9 (Documentation of statistical methods) of the CSR.

Appendix 16.1.9 text will contain details of statistical methods and issues that are more detailed than would be included in the CSR text. It is written in the future tense. It will be reviewed and updated (including conversion to past tense) for entry into the clinical study report after the analysis has taken place.

The detailed statistical methodology is similar to the RAP module 3 addendum 2 for the primary clinical study report (CSR) which is stored in the CREDI folder: *CREDI Projects/L/LDK378/CREDI Studies/LDKA2109/Administrative Files (study level)/RAP or RAMP Meeting*, except for the changes noted in the document history.

1.2 References

The following documents are used or referred to for the RAP generation:

- Clinical Trial Protocol CLDK378A2109 amendment version 03 (07Oct, 2015)
- Casebook CLDK378A2109 version 02 (05Aug, 2015)

2 Study objectives and study design

2.1 Primary objectives

- To characterize the pharmacokinetics of LDK378 in Chinese adult patients with ALK-rearranged NSCLC previously treated with crizotinib following single and multiple daily oral doses of LDK378.
- To assess the safety and tolerability of LDK378 after continuous 750 mg once daily dose in Chinese adult patients with ALK-rearranged NSCLC.

2.2 Secondary objectives

2.2.1 Key secondary objective

- To demonstrate the antitumor activity of LDK378, as measured by overall response rate (ORR) to LDK378 by investigator assessment.

2.2.2 Other secondary objectives

[figure not shown]
To evaluate response related endpoints as assessed by the investigators per RECIST 1.1:

- Duration of response (DOR)

CONFIDENTIAL - For Business Use Only

- Disease control rate (DCR)
- Time to Response (TTR)
- Overall intracranial response rate (OIRR)
- Progression-free survival (PFS)
- Overall survival (OS)

ORR and OIRR will also be evaluated as assessed by Blind Independent Review Committee (BIRC).

2.4 Study design

This is a phase I/II, open-label, multi-center study to assess the PK, safety, tolerability and efficacy of LDK378 in adult Chinese patients with locally advanced or metastatic NSCLC harboring a confirmed ALK rearrangement. Patients must have demonstrated progression during or after crizotinib treatment whether or not previously treated with cytotoxic chemotherapy and have no available ALK-targeted treatment options.

Overall approximately 100 patients will be enrolled in the study. The first 15 enrolled patients will enter a 5-day PK run-in period during the phase I component of this study. They will have PK sampling over 120-hour during the run-in period following a single oral dose at 750 mg. Additional patients may be enrolled in the study with the 5-day PK run-in period in case PK profiles from some of the enrolled patients are deemed not evaluable

The phase II component of the study will start on Cycle 1 Day 1 for all enrolled patients. During this period LDK378 will be given as continuous daily oral dosing at 750 mg QD in 28 -day cycles.

[figure not shown]
Extensive PK assessment will be collected for the first 15 enrolled patients to obtain approximately 12 evaluable full profiles. Sparse PK samples will be collected for the rest of patients. Adverse events will be collected at every visit after informed consent obtained. Laboratory assessment including hematology and blood chemistry will be taken at screening, run-in Day 1 for the first 15 enrolled patients, Day 1, Day 8, Day 15 for cycle 1 and Day 1 for subsequent cycles. Separate ECG monitoring schedules will also be collected for patients with extensive PK assessment and those with sparse assessment.

[figure not shown]
Tumor response will be evaluated every 8 weeks (i.e. every 2 cycles) starting from the first day of treatment with LDK378 until the time of RECIST-defined Progressive disease (PD) by investigator assessment, withdrawal of consent for further follow-up, loss to follow-up or death. This schedule of tumor assessment will continue regardless of dose interruptions. For patients who discontinue treatment in the absence of progression, tumor assessments will continue every 8 weeks until progression of disease, withdrawal of consent for further follow-up, loss to follow-up or death.

Treatment with LDK378 will continue until the patient experiences a RECIST-defined PD on LDK378 as assessed by the investigator, an unacceptable toxicity that precludes further treatment, discontinues treatment at the discretion of the patient or investigator, starts a new anti-cancer therapy or dies. Please refer to [Figure 1-1](#) for flow chart of the study design.

If the patient experiences RECIST-defined progressive disease (PD), treatment with the study drug may be continued if, in the judgment of the investigator, there is still evidence of clinical benefit. When the patient discontinues from study treatment an End of Treatment (EoT) visit must be performed within 7 days of the last dose of LDK378. Patients will be contacted for the safety follow-up 30 days after their last dose of LDK378. Following the cessation of tumor follow-up assessments, patients will be contacted every 3 months to determine survival status and/or whether the patient started any other antineoplastic therapies since discontinuing study treatment.

Figure 2-1 **Study design**

2.5 Study flow and visit schedule

See Table 7-1 in the protocol.

3 Draft of Section 9.7 of CSR - Statistical methods planned in the protocol and determination of sample size

3.1 Draft of Section 9.7.1 of CSR - Statistical and analytical plans

3.1.1 Definitions

3.1.1.1 Study drug and study treatment

Study drug and study treatment both refer to LDK378 and will be used interchangeably.

3.1.1.2 Date of first/last administration of study drug

The date of first administration of study drug is defined as the first date when a non-zero dose of study drug is administered and recorded on the Dosage Administration Record (DAR) electronic Case Report Form (eCRF). For the sake of simplicity, the date of first administration of study drug will also be referred as start date of study drug.

The date of last administration of study drug is defined as the last date when a non-zero dose of study drug is administered and recorded on the DAR eCRF. This date is also referred as last date of study drug.

3.1.1.3 Duration of exposure and Intensity

Definitions of duration of exposure, cumulative dose, average daily dose, actual dose intensity (DI), planned dose intensity (PDI), relative dose intensity (RDI), as well as intermediate calculations, include:

- Duration of exposure (days): last date of study drug – first date of study drug + 1 (periods of interruption are not excluded)
- Cumulative dose (mg): total dose of study drug taken by a patient in the study

- Number of dosing days (days): duration of exposure – number of zero dose days
- Average daily dose (mg/day): cumulative dose (mg)/number of dosing days, drug free day(s) in PK run-in period are not counted
- DI (mg/day): cumulative dose (mg)/duration of exposure (days)
- PDI (mg/day): cumulative planned dose (mg) / duration of exposure (days)
- RDI (%): $100 \times DI \text{ (mg/day)} / PDI \text{ (mg/day)}$

The cumulative planned dose is defined as the total planned dose according to the planned dosing schedule during the study treatment exposure. It is therefore calculated as follows: cumulative planned dose (mg) = protocol planned dose of 750 (mg)* duration of exposure.

For the first 15 patients who are planned to receive a single dose during the PK run-in period (of 5 days), and patients receive daily dosing thereafter, the cumulative planned dose is calculated as follows:

Cumulative planned dose (mg) =

- 750 (mg) * (duration of exposure -4), if duration of exposure (day) >5
- 750 (mg), if duration of exposure (day) ≤5

The similar procedure for calculation is applied to calculation of dosing days for the first 15 patients enrolled in the PK run-in period;

Number of dosing days (days) =

- duration of exposure – (number of zero dose days + 4), if duration of exposure (day) >5
- duration of exposure, if duration of exposure (day) ≤5

3.1.1.4 Dose interruption and dose change

Dose interruption and dose change will be listed and summarized as reported in the DAR eCRF.

Dose reductions are a subset of dose changes where dose changes to higher than protocol planned dose are excluded.

3.1.1.5 Study day

The study day for all assessments (e.g. tumor assessment, death, disease progression, tumor response, performance status, adverse event onset, laboratory abnormality occurrence, vital sign measurement, dose interruption) will be calculated using the start date of study drug as the origin. This also applies to patients who received single dose at PK run-in period. For assessments occurring after or on the start date of study drug, study day will be calculated as:

Study Day = Event date - start date of study drug + 1.

The first day of study drug is therefore study day 1.

For any assessment or events such as baseline disease characteristics or medical history (e.g., time since diagnosis of disease) occurring prior to the start of the study drug, study day will be negative and will be calculated as:

Study Day = Event date - start date of study drug.

CONFIDENTIAL - For Business Use Only

The study day will be displayed in the data listings.

3.1.1.6 Baseline

Baseline is the result of an investigation describing the “true” uninfluenced state of the patient. The last available assessment before or on the start date of study drug is defined as “baseline” value or “baseline” assessment. For cases when the assessment is planned to be performed before the first dose of study drug and the assessment is performed on the same day as the first administration of study drug:

- If either the assessment or first dose time point is not collected or is missing, it will be assumed that the assessment was performed prior to study drug administration.
- If both assessment and first dose time points are collected, the observed time point will be used to determine pre-dose on study day 1 for baseline calculation.

Unscheduled assessments will be used in the determination of baseline unless otherwise specified. Patients who start treatment and discontinue from the study on the same day may have two different sets of data collected on study day 1, one being reported to the cycle 1 day 1 visit (or PK run-in day 1 visit), the other reported to the end of treatment (EOT) visit. Data reported at the EOT visit are not eligible for baseline selection.

Laboratory data

If both central and local laboratory assessments are performed on the same date and corresponding to the baseline assessment date, then the central laboratory assessment will be used for the calculation of baseline.

ECGs

Baseline for each ECG measurement is the average of the pre-dose replicate measurements on the baseline day. Unscheduled assessments will not be included in the calculation of the average. Study day 1 (PK run-in day 1 for the first 15 patients and Cycle 1 day 1 for the rest patients) scheduled pre-dose ECGs will be considered to have been obtained prior to study drug administration if dosing time or ECG time is missing.

If a scheduled pre-dose measurement actually occurred post-dose, then the corresponding measurement will be treated and analyzed the same as an unscheduled post-dose measurement. For unscheduled assessments on study day 1, if dosing time is non-missing, then the assessment is considered as post-baseline if ECG collection time is later than dosing time. If dosing time is missing, these unscheduled assessments will be considered as post-baseline.

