3.2.9.4 Vital signs

Vital sign assessments will be performed in order to characterize basic body function. The parameters collected are weight (kg), body temperature (°C), pulse rate (beats per minute), systolic and diastolic blood pressure (mmHg).

Clinically notable elevated values are defined as:

- Systolic BP: \geq 160 mmHg and an increase \geq 20 mmHg from baseline
- Diastolic BP: \geq 100 mmHg and an increase \geq 15 mmHg from baseline.
- Body temperature: \geq 39.1°C
- Weight: increase from baseline of \geq 10%
- Pulse rate: \geq 120 bpm with increase from baseline of \geq 15 bpm

Clinically notable below normal values are defined as:

- Systolic BP: \leq 90 mmHg and a decrease \geq 20 mmHg from baseline
- Diastolic BP: \leq 50 mmHg and a decrease \geq 15 mmHg from baseline
- Body temperature: \leq 35°C
- Weight: decrease from baseline of \geq 10%
- Pulse rate: \leq 50 bpm with decrease from baseline of \geq 15 bpm

Vital signs shift table based on values classified as notable low, normal, notable high or notable (high and low) at baseline and worst post-baseline will be produced for pulse rate, diastolic BP and systolic BP.

Descriptive statistics will be tabulated for baseline and change from baseline to worst post-baseline value for each vital sign measurement.

Patients with at least one clinically notable vital sign abnormalities will be listed. All vital sign assessments will be listed by patient and vital sign parameter.

In the listings, clinically notable values will also be flagged.

WHO performance status

ECOG performance scale is provided in [Table 3-2](#) and is used to assess physical health of patients, ranging from 0 (most active) to 5 (dead):

Table 3-3 WHO performance scale

Score	Performance Status
0	Fully active, able to carry on all pre-disease performance without restriction
1	Restricted in physically strenuous activity but ambulatory and able to carry out work of a light or sedentary nature, e.g. light house work, office work
2	Ambulatory and capable of all self-care but unable to carry out any work activities. Up and about more than 50% of waking hours
3	Capable of only limited self-care, confined to bed or chair more than 50% of waking hours
4	Completely disabled. Cannot carry on any self-care. Totally confined to bed or chair
5	Dead

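### The SAP's baseline rule, read literally, lets an unscheduled Day 1 vital sign (and some laboratory values) taken after the first dose serve as baseline

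*SAP*

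**What the plan says.** SAP 3.1.1.6 opens by describing baseline as the "uninfluenced state of the patient". Its working rule is set by date: "The last available assessment before or on the start date of study drug is defined as" baseline. A same-day rule follows, limited to assessments "planned to be performed before the first dose of study drug and the assessment is performed on the same day" as the first dose:

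- Both times known: "If both assessment and first dose time points are collected, the observed time point will be used to determine pre-dose on study day 1".
- Either time missing: "it will be assumed that the assessment was performed prior to study drug administration".

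The section then states: "Unscheduled assessments will be used in the determination of baseline unless otherwise specified". Three special provisions follow:

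- End-of-treatment data recorded on Day 1 cannot be baseline.
- If central and local laboratory results fall on the same baseline date, the central one is used.
- An unscheduled Day 1 ECG is post-baseline if it was recorded after dosing. For a missing dosing time the rule is: "If dosing time is missing, these unscheduled assessments will be considered as post-baseline".

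Elsewhere, protocol 10.5.3.1 takes baseline for shift and change summaries from the pre-treatment period, which ends the day before first dose. SAP 3.2.9 says only that such data may be used. SAP 3.2.2 requires the demographic baseline weight to precede first administration. SAP 4.1.1 records no difference between SAP and protocol.

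**The concern.** An unscheduled assessment is not one that was planned pre-dose, so the clock-time check does not reach it. The date rule and the eligibility sentence do. A blood pressure or pulse taken some hours after the first dose is then the last value on the start date, and becomes the reference even when its recorded time shows that it followed dosing.

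Safety and tolerability is a primary objective, and several safety outputs are measured against baseline. SAP 3.2.9.4, for example, plans this: "Descriptive statistics will be tabulated for baseline and change from baseline to worst post-baseline value for each vital sign measurement". The ECG and end-of-treatment provisions show that the authors recognised post-dose contamination on Day 1 and closed it in two places. Vital signs and part of the laboratory data were left open.

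**Working it through.** The plan states no figure on this point, so the check is textual, followed by illustrations.

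**Step 1. Which values the literal rule admits on Day 1**

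| Type of Day 1 value | Rule that applies | Can a post-dose value be baseline? |
|---|---|---|
| Scheduled pre-dose, both times known | Observed time | No |
| Scheduled pre-dose, a time missing | Assumed pre-dose | Only if the assumption is wrong |
| Unscheduled ECG | ECG paragraph | No, if taken after dosing or dosing time is missing |
| Unscheduled local laboratory test, central sample the same day | Central result preferred | No |
| Unscheduled laboratory test, no other central sample that day, or itself sent centrally | Date rule only | Yes |
| Unscheduled vital sign | Date rule only | Yes |

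**Step 2. What happens to the outputs**

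The patient values below are assumed. The criteria come from SAP 3.2.9.4 (pulse low: at most 50 bpm with a fall of at least 15; systolic high: at least 160 mmHg with a rise of at least 20) and from the grade limits in protocol Table 6-3.

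- Pulse 78 pre-dose, 52 post-dose, later 50. Change from pre-dose: 50 − 78 = −28, notable. From post-dose: 50 − 52 = −2, not notable. The event is missed.
- Systolic 135 pre-dose, 145 post-dose, later 162. From pre-dose: 162 − 135 = 27, notable. From post-dose: 162 − 145 = 17, not notable. The event is missed.
- Systolic 145 pre-dose, 135 post-dose, later 160. From pre-dose: 160 − 145 = 15, not notable. From post-dose: 160 − 135 = 25, notable. The event is falsely counted.
- Creatinine 0.8 × ULN pre-dose, 0.95 post-dose, later 1.3. From pre-dose: 1.3 / 0.8 = 1.63, above 1.5, grade 2. From post-dose: 1.3 / 0.95 = 1.37, grade 1.
- ALT 0.9 × ULN pre-dose, 1.2 post-dose. If the later worst value is 1.5, it is a new abnormality (grade 0 to 1) against the pre-dose value and not new (1 to 1) against the post-dose value. If the later worst value is 6, the worst grade is 3 either way, and only the row of the shift table changes.

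**Step 3. Loss from the worst-value pool**

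SAP 3.1.5.1 bases worst-value analyses on all post-baseline values, including unscheduled ones. Take pulse 78 pre-dose, 48 unscheduled post-dose and 60 thereafter. Classified correctly, 48 is notable (a fall of 30). If 48 is baseline, no notable value is counted.

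**Step 4. How many patients**

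The documents do not say. Assuming 0% to 5% of the 103 treated patients: 103 × 0 = 0 and 103 × 0.05 = 5.15, so 0 to about 5 patients, or at most 5 percentage points in any one table.

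**The case against.** The strongest reply is that the intent is clear. The section aims at an uninfluenced state, uses observed times to decide pre-dose status, and sits under a protocol that takes baseline from before treatment. That is fair, and a reader who infers that the sponsor means to use drug-affected baselines goes further than the documents allow. But the operative wording still produces one, and SAP 3.2.9 weakens the protocol sentence that would prevent it.

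A second reply stands in large part. Most of the laboratory exposure is already covered. Protocol 7.2.2.5 has scheduled blood tests analysed centrally and allows local unscheduled tests when a decision is urgent; SAP 2.4 schedules laboratory assessments on the first dosing day. A same-day local test therefore usually loses to the central one. The remainder is a patient with no central Day 1 sample (protocol 7.1.2 does not require screening tests to be repeated before dosing) or an unscheduled sample sent centrally.

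Third, heart rate is also captured by scheduled ECGs around 4 and 6 hours, or 2–4 and 5–7 hours, after the first dose. These are compared with a baseline averaged over scheduled pre-dose replicates, and bradycardia is summarised as an AE of special interest. This limits the consequence for pulse but does not correct the blood pressure or weight tables.

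A reader might also infer that later toxicity is systematically under-counted, or that the post-dose value disappears. Neither is supported. The third example in the working is an over-count, and the value remains listed and dated within the on-treatment period. Nothing in the documents shows that unscheduled Day 1 assessments are common, or that they cluster in unwell patients.

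**Conclusion.** The point holds as a defect in a stated rule with limited reach. The rule admits a post-dose reference value for unscheduled Day 1 vital signs and for a residue of laboratory tests. In those patients, notable blood pressure, pulse and weight, creatinine-type grades, shift tables and new or worsened laboratory abnormalities can be misclassified in either direction. In addition, a post-dose value used as baseline can no longer count as the worst post-baseline value. Weight can have two baselines, one under SAP 3.2.2 and another under 3.1.1.6.

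The number affected is unknown, possibly zero and probably small. The 0 to 5 patients above rest on an assumed 0% to 5% and on nothing in the documents. All affected outputs are descriptive. The conclusion also assumes that programmers apply the text as written; one who follows the stated aim would avoid the error.

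**What to change.** Amend SAP 3.1.1.6 to say that any Day 1 assessment, scheduled or unscheduled, is eligible for baseline only if taken before the first dose, judged by recorded times where both exist. Keep the presumption that a missing time means pre-dose only for assessments scheduled pre-dose. Do not use an unscheduled Day 1 value with either time missing as baseline. This goes slightly beyond the ECG rule, which covers only a missing dosing time. State whether such a value is then counted as post-baseline or only listed.

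Reconcile SAP 3.1.1.6 and 3.2.9 with protocol 10.5.3.1. Taken literally, the protocol sentence would also exclude a genuine pre-dose Day 1 value, so the reconciled text should say that such a value is allowed.

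The cost is a sentence or two and a change to the programmed baseline indicator. Protocol 6.1.1.1 requires the dosing time to be recorded on PK days, which include the first-dose day. The documents do not show whether clock times are recorded for unscheduled vital signs and laboratory tests. If they are not, a true pre-dose unscheduled value would not be used as baseline and, if counted as post-baseline, could appear treatment-emergent.
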